2.2 Analysis sets

Participants will be analyzed according to either the treatment(s) received or to the assigned treatment sequence, depending on the analysis.

The enrolled set will include all participants who signed an ICF, including screen failures.

The safety analysis set will include all participants that received any study treatment.

The PK analysis set will include all participants with at least one available valid (i.e., not flagged for exclusion) PK concentration measurement, who received any study treatment and had no protocol deviations with relevant impact on PK data.

The PD analysis set will include all participants that received study treatment and had no protocol deviations with relevant impact on PD data.

Details on pharmacokinetic analysis

Concentrations that should not be included in the descriptive statistics (summaries or figures) may be flagged by the pharmacokineticist at the time of the final pharmacokinetic analysis. These concentrations will remain in the listings along with an explanation for the exclusions (provided by the pharmacokineticist).

Analysis set exclusions based on Protocol Deviations

Protocol deviations will be reviewed case by case to select any participant to be excluded from an analysis set taking also into account the rules defined in [Table 1-2](#).

Withdrawal of Informed Consent

Any data collected in the clinical database after a participant withdraws informed consent from all further participation in the trial, will not be included in the analysis. The date on which a participant withdraws full consent is recorded in the eCRF.

2.2.1 Subgroup of interest

Participants will be divided into 2 subgroups of interest according to CHIP type (*TET2* or *DNMT3A*).

Summary statistics by subgroup will be provided for the main analyses.

2.3 Patient disposition, demographics and other baseline characteristics

2.3.1 Patient disposition

Disposition at screening, including those who completed screening and were treated, those who completed screening and were not treated, and reasons for those not completing screening will be displayed for the enrolled set.

Participant disposition will be presented using the Safety set for treatment sequence and all participants. The following summaries will be provided:

- Number (%) of participants who completed treatment and those who discontinued the study treatment phase along with the primary reason for study treatment discontinuation (based on the 'End of Treatment' disposition page)

Participant disposition data will be listed by treatment sequence.

2.3.2 Demographics and other baseline characteristics

The Safety analysis set will be used for all baseline and demographic summaries and listings. Demographic summaries will be presented by actual treatment sequence.

Demographic parameters (Age, Sex, Race, Ethnicity, Height, Weight, and BMI) and main baseline characteristics: CHIP type, CYP2C9 genotype, hsCRP, IL-6, IL-18, Systolic and Diastolic Blood Pressure, LDL Cholesterol, Estimated GFR expressed in numerical and categorical (grades) terms will be summarized descriptively and listed.

Time (years) from last episode of Myocardial infarction (MI) will be derived as a further baseline characteristic, looking at data collected in the medical history form.

Episodes will be detected by considering events coded as ‘Acute myocardial infarction/ Myocardial infarction and time in years from last MI will be derived as: (day 1 – date of MI +1)/365.25.

The following categories will be reported:

Not available, <= 1year, >1 to <=5 years, >5 to <=10 years, > 10 years.

Incomplete dates will be managed as indicated in [Section 5.1.3.3](#)

ST-elevation (not available / STEMI/ non STEMI) will also be reported looking at the lower level term code.

Relevant medical histories and current medical conditions at baseline will be listed by system organ class and preferred term, by treatment sequence and participant. A summary table by treatment sequence will also be provided.

2.3.3 Protocol deviations

All important protocol deviations will be listed. A summary table by treatment sequence and deviation category will be provided if appropriate.

2.3.4 Analysis sets membership

The number (%) of participants randomized and included in each analysis set (defined in [Section 2.2](#)) will be summarized by treatment sequence and treatment separately.

2.4 Treatments (study treatment, rescue medication, concomitant therapies, compliance)

2.4.1 Study treatment / compliance

Study treatment compliance will be descriptively summarized by study treatment for the safety analysis set, including compliance in different percent categories, (< 20%, between 20% and < 40%, between 40% and <60%, between 60% and < 80%, >= 80%) as derived considering protocol deviation codes. This analysis will be performed in terms of dosing sessions considering a potential sample size of twenty-four 3-week dosing sessions with placebo. Note that treatments with MAS825 and DFV placebo won't be included in this analysis being assigned to MAS825 treatment.

Study treatment duration (in days), defined as last date of administration – first date of administration +1, will also be summarized by treatment.

Compliance data will also be listed by treatment sequence.

This analysis will be restricted to DFV890/DFV890 placebo sessions excluding the participants randomized to the first treatment sequence.

Details regarding MAS825, MAS825 placebo, DVF890 placebo administrations in participants treated previously with MAS825, will be only listed by treatment sequence and treatment.

2.4.2 Prior, concomitant and post therapies

Concomitant medications and significant non-drug therapies prior to and after the start of the study treatment will be listed according to the Anatomical Therapeutic Chemical classification system by treatment sequence for the safety analysis set.

Concomitant medications, defined as medications started before Day 1 and still ongoing at Day 1, will also be summarized by treatment sequence.

Pre-treatment (non-drug) procedures will be summarized by treatment sequence.

2.5 Analysis supporting primary objective(s)

The primary objective is to evaluate the effect of various dose levels of DFV890 versus placebo to reduce circulating levels of inflammatory markers (IL-6 and IL-18) in participants with coronary heart disease and CHIP. The effect of a single dose of MAS825 vs placebo, as well as a comparison between MAS825 and DFV890 (IL-6 only) will be also evaluated.

2.5.1 Primary endpoint(s)

The primary endpoints are the change from baseline in log transformed serum levels of IL-6 and IL-18 at 3 weeks after the start of a dosing period. Screening and follow-up assessments will be listed and summarized, while the statistical analysis, described in the next section, will include only the assessments taken at the end of each dosing period and the baseline as a covariate. Individual plots by treatment and by treatment sequence will also be provided.

Summaries of descriptive statistics by time will be provided by treatment and by treatment sequence. Summary statistics by sequence will also be used to investigate the presence of potential period/carry-over effects.

Descriptive analyses will also be provided by subgroup (see [Section 2.2.1](#)).

The definition of the primary estimand is provided in [Section 1.2.1](#)

2.5.2 Statistical hypothesis, model, and method of analysis

The primary analysis will assess the effect of DFV890 on the change from baseline in log transformed IL-6 and IL-18 values, compared to placebo in a dose-response model, separately for the two biomarkers. In this analysis, MAS825 data are excluded from the analysis (including placebo sessions following a MAS825 dose).

For each biomarker, an E_{\max} model will be fit to the change from baseline, with a random effect (reflecting between-participant variability) on the placebo response E_0 and on ED_{50} (the dose that produces half the maximal effect), a covariate on E_0 for the baseline value of the biomarker, and a covariate on ED_{50} for baseline body weight. All biomarker measurements will be logarithm-transformed prior to the analysis. Baseline biomarker value and body weight will also be log transformed and centered using the median value over the patients included in the model.

Strategy in case of convergence issue.

If the above described model fails to converge other methods will be assessed such as:

Model 2= a model without the random effect on ED_{50} (2 covariates ,1 random effect).

Model 3 = a model removing the covariate on ED₅₀ (1 covariate, 2 random effects)

Model 4 = a model removing both the covariate and the random effect on ED₅₀ (1 covariate and 1 random effect).

Model 5 = a traditional linear model including treatment as a fixed categorical effect, a random intercept effect for participant, and the baseline value of the biomarker and baseline body weight as covariates. Only for IL6 this model will also include MAS825 sessions, managed as 4 different treatment groups (MAS 3w, MAS 6w, MAS 9w, MAS 12w).

An additional random effect reflecting between-participant variability on E_{max} may be incorporated if the data allows.

From each model, the predicted response at each treatment and associated 80% confidence interval (CI) will be extracted, along with the difference to placebo for each DFV890 dose level, the corresponding 2-sided 80% CI, and the p-value. The estimated response and the difference to placebo will be back-transformed and reported on the ratio scale.

From the model-based quantities, the following efficacy criteria will be evaluated at the log transformed median value of the biomarker and of body weight:

1. At least one of the following is observed in relation to placebo at the 100 mg dose:
 - IL-6 reduction $\geq 25\%$, or
 - IL-6 reduction $\geq 20\%$ + IL-18 reduction $\geq 10\%$, or
 - IL-6 reduction $\geq 15\%$ + IL-18 reduction $\geq 20\%$.
2. For any of the above criteria that are achieved, the one-sided p-value for the comparison of DFV890 vs. placebo for the associated biomarker(s) is less than 0.1.

A plot showing predicted responses at each treatment and associated 80% confidence interval (CI) as well as the observed mean response will be provided for the selected and the traditional model.

The evaluation of the MAS825 effect will be based on the model described as model 5. This will include a comparison of MAS825 effects vs placebo and comparisons of each DFV890 dose vs MAS825 3 week effect.

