The study statistician will be able to access the randomization list at any time throughout the study and is allowed to share unblinded information with the rest of the clinical team as appropriate for internal decision making purposes, as outlined in [Table 6-4](#). For example, unblinded summaries and unblinded individual data can be shared with the team for interim analyses.

Study programmers and other personnel involved in study data analyses (e.g., biomarker expert, pharmacometrician, and potentially others) are also allowed to access treatment assignment information at any time throughout the study for the purpose of conducting data analyses.

The clinical trial team (CTT) is allowed to share unblinded results with other sponsor staff (e.g., decision boards) as required for internal decision making on the study or the project at the time of interim analyses while the study is ongoing.

All unblinded personnel will otherwise keep randomization lists and data or information that could unblind other study team members confidential and secure except as described above.

Following final database lock, all roles may be considered unblinded.

Table 6-4 Blinding and unblinding plan

Role	Time or Event			
	Randomization list generated	Treatment allocation & dosing	Safety event (single subject unblinded)	Interim Analysis/ dose escalation/ safety review
Participants	B	B	UI	B
Site Staff	B	B	UI	B
Global Clinical Supply	UI	UI	UI	UI
Randomization Office	UI	UI	UI	UI
Statistician/statistical programmer/ data analysts (e.g. biomarker, PK)	B	UI	UI	UI
Unblinded site staff, e.g. pharmacy staff	B	UI	UI	UI
Unblinded Sponsor staff, e.g. for study treatment re-supply, unblinded monitor(s), sample analyst(s)	B	UI	UI	UI
Sponsor CTT	B	B	UI	UI
All other Sponsor staff not identified above (i.e. project team, management & decision boards, support functions)	B	B	UI	UI

B Complete blinded

UI Unblinded to individual participant treatment codes

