9.3.2 Statistical model, hypothesis, and method of analysis

The primary analysis for DFV890 will assess the effect on the change in IL-6 and IL-18 compared to placebo in a dose-response model, separately for the two biomarkers.

An E_{\max} model will be fit to the post-baseline values for each biomarker, with a random effect (reflecting between-participant variability) on the placebo response E_0 and on ED_{50} (the dose that produces half the maximal effect), a covariate on E_0 for the baseline value of the biomarker, and a covariate on ED_{50} for baseline body weight. All biomarker measurements will be logarithm-transformed prior to the analysis.

An additional random effect reflecting between-participant variability on E_{\max} may be incorporated if the data allows.

Additional details of the model will be specified in the Statistical Analysis Plan (SAP).

From the model, the predicted response at each treatment and associated 80% CI will be extracted, along with the difference to placebo for each DFV890 dose level, the corresponding 2-sided 80% CI. The estimated response and the difference to placebo will be back-transformed and reported on the ratio scale.

In case of convergence issues, a linear mixed effects model will be fit in place of the E_{\max} model (to be referred to as 'traditional model'). The model will include treatment as a fixed effect, a random intercept effect for participant, and the baseline value of the biomarker and baseline body weight as covariates. All biomarker measurements will be logarithm-transformed prior to the analysis.

The least square (LS) mean and associated 80% CI for each treatment, and the estimated mean difference to placebo for each DFV890 dose level and 2-sided 80% CI will be extracted from the model and back-transformed to the ratio scale for reporting.

The primary analysis for MAS825 will assess the effect on the change in IL-6 compared to placebo after 3 weeks of treatment. For this analysis, the Week 3 measurements of IL-6 on MAS825 and all Week 3 (i.e., Dosing Period 1) placebo measurements from the other sequences will be used.

A linear model of IL-6 at Week 3 with treatment as a fixed effect, and the baseline value of the biomarker as a covariate will be used for the analysis. All biomarker measurements will be logarithm-transformed prior to the analysis.

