2.5.5 Sensitivity analyses

As a sensitivity analysis to the Emax model described in [Section 2.5.2](#), a Hill coefficient other than 1 may be explored.

If the Emax model converges on either of the two primary endpoints, the traditional model previously described will be performed as a sensitivity analysis on that endpoint and/or to assess MAS825 effect.

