The assumed true E_{max} is approximately -0.5, or $\log(0.6)$, representing a 40% reduction.

From the model-based quantities, the following efficacy criteria will be evaluated at the median baseline value of the biomarker and the median baseline body weight:

1. At least one of the following is observed in relation to placebo at the 100 mg dose:
 - IL-6 reduction \geq 25%, or

- IL-6 reduction $\geq 20\%$ + IL-18 reduction $\geq 10\%$, or
 - IL-6 reduction $\geq 15\%$ + IL-18 reduction $\geq 20\%$.
2. For any of the above criteria that are achieved, the one-sided p-value for the comparison of DFV890 vs. placebo for the associated biomarker(s) is less than 0.1.

Simulations have shown that there is at least 80% power in achieving statistical significance at the 10% level and the mean effect as shown above (with type 1 error of $\leq 10\%$)

This allocation of participants will also provide at least 80% power of showing a statistically significant difference between MAS825 and pooled placebo, if the true effect of MAS825 on IL-6 is a 45% reduction (i.e., $\log(0.55)=0.60$, there is no effect on placebo, and the between subject SD of IL-6 is ≤ 0.5 using a 1 sided alpha of 10%.)

If MAS825 is not different from placebo, there will be a 10% chance of achieving the efficacy criteria (Type 1 error).

4 Change to protocol specified analyses

This SAP is based on the analyses described in the study protocol. Additional details and clarifications have been introduced to provide a more accurate description of the statistical plan.

5 Appendix

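### Protocol 9.3.2 and SAP 2.5.2 give different fallbacks when the DFV890 Emax model fails to converge, and the SAP does not say which model decides the efficacy criteria

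*SAP*

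**What the plan says.** Protocol 9.3.2 specifies an Emax model for each biomarker, with random effects on E0 and ED50, a baseline covariate on E0 and a body-weight covariate on ED50. Its fallback is a single model: "In case of convergence issues, a linear mixed effects model will be fit in place of the" Emax model. This is the protocol's traditional model: categorical treatment, random participant intercept, baseline biomarker and body weight.

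SAP 2.5.2 keeps the same starting model but words the fallback differently: "If the above described model fails to converge other methods will be assessed such as", followed by four entries:

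- Model 2 drops the random effect on ED50.
- Model 3 drops the weight covariate on ED50.
- Model 4 drops both.
- Model 5 is the linear mixed model. For IL-6 only, it also takes in the MAS825 sessions as four extra treatment groups.

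On output, the SAP states that "From each model, the predicted response at each treatment and associated 80% confidence interval (CI) will be extracted". The efficacy criteria are then read from model-based quantities, without saying from which model. A plot "will be provided for the selected and the traditional model", but no selection rule is given. SAP 2.5.5 adds that, if the Emax model converges, "the traditional model previously described will be performed as a sensitivity analysis on that endpoint". It does not say whether a reduced Emax model counts as the Emax model for this purpose.

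SAP Section 4, on changes to protocol analyses, states: "This SAP is based on the analyses described in the study protocol". It continues: "Additional details and clarifications have been introduced to provide a more accurate description of the statistical plan". The fallback is not mentioned.

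**The concern.** The go decision for DFV890 rests on explicit criteria: point estimates at 100 mg, each with a one-sided p-value below 0.1. If the starting model fails, the protocol leads to one result. The SAP can lead to any of four, and to different models for IL-6 and IL-18. For a modest effect these results need not agree, and neither document says which one counts.

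Blinding does not protect the choice. Protocol 6.3.2 says that "The study statistician will be able to access the randomization list at any time throughout the study", and SAP 2.13 provides for an unblinded ad hoc interim assessment that looks, among other things, at Emax compatibility and convergence. The deciding model should therefore be fixed in writing first.

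**Working it through.** **Inputs from the documents.** Sequences 2 to 5 (SAP 2.1.1.2) have 8, 8, 2 and 2 participants (Protocol 9.9.1). That is 20 participants and 20 × 4 = 80 sessions: 24 placebo (matching the count in SAP 2.4.1), 10 at 10 mg, 18 at 25 mg, 10 at 50 mg and 18 at 100 mg. True ED50 is 20 mg, IL-6 within-subject SD is 0.4 on the log scale, the markers are independent, and the criteria are those of Protocol 9.9.1.

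**Assumptions not in the documents.** Between-subject SD 0.3 (range to 0.5), SD of log ED50 0.3 (to 0.5), IL-18 within-subject SD 0.25 (to 0.35; the plan says only that it is below IL-6), SD of log weight 0.2, dropout 0 (to 10% per active period).

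**Model.** Log response = E0 + Emax × dose / (ED50 + dose) + error. The planned 30% reduction is taken as the effect at 100 mg: log(0.7) = −0.357 = Emax × 100/120, so Emax = −0.428. The plan also quotes Emax as log(0.6). That gives −0.511 × 100/120 = −0.426, a reduction of about 35%, and power of 96 to 98%. The lower effect is used below.

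**Results.** There were 800 simulated trials for the first and last rows and 600 for the others. Models 1 to 4 were fitted by maximum likelihood and Model 5 by REML. Model 5 here is the linear mixed model without MAS825 sessions. Entries are percentages of trials.

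| True effect at 100 mg | Model 2 passes | Model 3 | Model 4 | Model 5 | Models 2–5 not unanimous | Models 4 and 5 opposite |
|---|---|---|---|---|---|---|
| 30% on both markers | 94 | 91 | 95 | 90 | 10 | 5 |
| Same, upper end of the SD ranges, 10% dropout | 92 | 86 | 91 | 82 | 18 | 10 |
| IL-6 20%, IL-18 10% | 48 | 44 | 45 | 38 | 23 | 16 |
| None | 2.6 | 2.2 | 2.5 | 1.8 | 2.6 | 1.5 |

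The Monte Carlo standard error is √(0.05 × 0.95 / 800) ≈ 0.8 points for the 5% entry and √(0.16 × 0.84 / 600) ≈ 1.5 points for the 16% entry.

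1. *The plan's own figures.* At least 80% power and at most 10% type 1 error are reproduced under every model.
2. *Size of the disagreement, Model 4 against Model 5.* Further simulations with other assumed SDs (for example IL-6 between-subject SD 0.5, IL-18 within-subject SD 0.3) gave 5 to 6% at a 30% reduction and 12 to 18% at 15 to 20%.
3. *Restricting to usable fits.* If Model 4 puts the IL-6 ED50 at the limit of its search range (1 to 400 mg), a sensible rule would call that a failure and pass to Model 5, as the protocol does. With an interior IL-6 ED50 required, the disagreement falls to about 2 to 3% and 7 to 11%.
4. *Restricting to trials where the fallback is used.* Among trials where Model 1 did not reach an interior solution with a positive-definite Hessian, Models 2 to 5 were not unanimous in 11%, 19%, 23% and 2% in the four rows.
5. *Free choice of model.* Taking any passing model among Models 2 to 5 lifts success from 38% (Model 5) to 54% in the third row, and from 1.8% to 3.6% under no effect.
6. *MAS825 sessions in Model 5.* Adding them for IL-6 changed the Model 5 verdict in 1.5%, 2.0%, 3.0% and 0.1% of trials in the four rows.

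**The case against.** The SAP's list sits under a heading on strategy for convergence problems and is numbered. ED50 terms are removed singly, then together, and the list ends at the protocol's type of model. That reads like a ladder. The protocol leaves further model details to the SAP and itself allows an extra random effect on Emax. The traditional model is to be shown whether or not an Emax model converges, so a conflict would be visible. The trial is an exploratory Phase 2a study.

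Much of this stands. It would be wrong to say that the SAP drops the protocol's fallback or hides disagreement. But a numbered list introduced as examples is not a stopping rule, and showing two results does not say which one decides. Leaving model details to the SAP does not obviously cover a different fallback when the protocol names the model to be fitted instead.

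A reader might infer three stronger things that are not supported:

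- *That the trial's error rate or power fails.* Even with the most favourable model picked, the false-positive rate was 3.6%, against a stated limit of 10%.
- *That non-convergence can be forecast.* In simulation the full Model 1 reached a clean interior solution for IL-6 in only about 14 to 18% of trials at the planned or larger effect. That is a strict proxy and depends on the optimiser and assumed variances. It shows that the fallback may well be needed, not how often.
- *That someone will choose by result.* The written trigger is convergence failure. Access to codes removes a safeguard but is not evidence about model choice.

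**Conclusion.** The two documents conflict on the fallback for the primary DFV890 analysis, the SAP does not say which model decides, and the change is undeclared. The stated power and type 1 error survive. The harm is that the efficacy verdict can depend on the model chosen. Comparing Models 4 and 5, this occurred in roughly 5% of simulated trials at a 30% reduction (10% with larger variability and dropout) and 12 to 18% at 15 to 20%. Among fits with an interior IL-6 ED50 the figures are about 2 to 3% and 7 to 11%. All of these rest on assumed between-subject and IL-18 SDs, a true ED50 of 20 mg and independent markers. Severity: should-fix.

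**What to change.** Amend SAP 2.5.2 before unblinded data are used to choose a model:

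1. Delete the words *such as*, so that the list is closed.
2. Define convergence, for example optimiser convergence plus a positive-definite Hessian. Do not reject a fit only because ED50 lies outside the studied doses: the criteria use the 100 mg contrast, which can be well estimated even when ED50 is not.
3. Either restore the protocol's linear mixed model as the sole fallback, or fix the order of Models 2 to 5 and stop at the first that converges, separately for each biomarker.
4. State that the efficacy criteria are read only from that model and that the others are sensitivity analyses. Align SAP 2.5.5 with this.
5. State whether the fallback model for IL-6 includes MAS825 sessions. SAP 2.5.2 first excludes them from the DFV890 analysis and then adds them in Model 5, so naming Model 5 as it stands would not restore the protocol's rule.
6. Declare whatever differs from the protocol in SAP Section 4.

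The cost is wording only, with no new data. If the linear mixed model becomes the sole fallback, some power is lost relative to Model 4: about 90% against 95% at the planned effect, and roughly 7 to 12 points at a 20% reduction. Power still stays above 80%: about 90% under the stated assumptions and 82% under the harsher ones.
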